7.2 PARTICIPANT DISCONTINUATION/WITHDRAWAL FROM THE STUDY

Participants are free to withdraw from participation in the study at any time and without having to give a reason. But if the subject is willing to give a reason for discontinuation or withdrawal from the study it will be recorded with the subject files. Subjects who sign the informed consent form and are not randomized will be replaced. Subjects who sign the informed consent form, are randomized, and receive the full study intervention (5 consecutive days of 40-minutes of stimulation), and subsequently withdraw or are withdrawn or discontinue from the study will not be replaced. However, subjects who sign the informed consent form, and are randomized and receive only part of the study intervention, and subsequently withdraw or are withdrawn or discontinue from the study will be replaced.

7.3 LOST TO FOLLOW-UP

A participant will be considered lost to follow-up if he or she fails to return for the scheduled follow-up visit and is unable to be contacted by the study site staff. All efforts will be made to ensure subjects are not lost to follow-up, including developing rapport and ensuring enrolled subjects are reminded of their session dates. To ensure that subjects attend the follow-up session, research personnel will be flexible in timing, including offering sessions later in the day as well as some weekends.

Every effort will be made to contact subjects who are lost to follow-up, including contacting via email and phone. However, if a subject is lost to follow-up, the missed sessions will be labeled as missing data and our pre-determined analysis plan takes into consideration missing data.

8. STUDY ASSESSMENTS AND PROCEDURES

8.1 EFFICACY ASSESSMENTS

Inclusion and exclusion criteria will be determined at the initial two session (pre-screening and screening), including concomitant therapies, medical history, and diagnoses, to ensure that subjects are diagnosed with MDD, with low suicide risk, and free of benzodiazepines and anticonvulsant medications.

8.1.1 PHYSIOLOGICAL CHANGES

1. Resting state EEG (RSEEG) recordings will be completed several times during the study. On every day of the intervention week, subjects will complete an eyes open resting-state EEG (RSEEG) immediately before and after the 40-minutes of stimulation. This measure is used to determine the immediate after-effects of tACS on brain activity, specifically on alpha oscillation power, as well as how consecutive stimulation sessions may affect these after-effects. RSEEG will also be recorded at the follow-up visit to determine the lasting effects of stimulation. An eyes-closed RSEEG will also be collected on Day 1 and at the follow-up visit.

8.1.2 CLINICAL EVALUATIONS

1. The M.I.N.I is a diagnostic tool that will be used during the screening session to confirm diagnosis of unipolar, non-psychotic MDD.
2. The Hamilton Depression Rating Scale 17-item (HDRS17) [12] will be administered during the initial session, day 1 of stimulation, day 5 of stimulation and during the 2-week follow-up visit. This scale is used to determine eligibility and to monitor the severity of the subject's depressive symptoms, as well as determine suicide risk.
3. The C-SSRS is a standardized method to access lifetime suicidality and current suicidal ideations and intends.
4. The Maudsley Staging Method is a method of measuring treatment resistance in subjects with depression on a scale of 3 to 15 (mild = 3-6; moderate = 7-10; severe=11-15)[16].
5. The Young Mania Rating scale (YMRS) to detect symptoms of mania and hypomania during the study.

8.1.3 SELF-REPORT ASSESSMENTS

1. The Beck Depression Inventory (BDI) [17], [18]will be administered at day 1, day 5 of stimulation and at the follow-up visit. The BDI is a 21-item, self-report rating inventory that measures characteristic attitudes and symptoms of depression and will be used to monitor the severity of the patient's depression throughout the study.
2. The inventory of Depression and Anxiety Symptoms (IDAS) [19] will be completed day 1 of stimulation, day 5 of stimulation and during the 2-week follow-up visit. This inventory is used to monitor the perceived severity of the subject's symptoms of depression.
3. The Quality of Life Enjoyment and Satisfaction Questionnaire, short form (Q-LES-Q-SF)[20], will be administered at day 1 of stimulation, day 5 of stimulation, and the 2-week follow-up visit. This self-report questionnaire assesses quality of life.
4. The Pittsburg Sleep Quality Index (PSQI) [21], [22] will be administered at day 1 of stimulation and the 2-week follow up visit. This self-report questionnaire assesses sleep quality over the course of the past month. It will be used to determine changes in sleep quality.

5. The WHO Disability Assessment Schedule 2.0 (WHODAS 2.0) [23], [24] will be administered at baseline to assess any comorbid disability that could potentially affect quality of life and/or response to stimulation.
6. The Behavioral Inhibition and Behavioral Activation Self Report Scales (BAS/BIS) [25] will be completed during day 1 of stimulation, day 5 of stimulation and during the 2-week follow-up visit. These scales are used to monitor the perceived sensitivity to reward and punishment.
7. The State-Trait Anxiety Inventory (STAI) [26] will be completed during day 1 of stimulation, day 5 of stimulation and during the 2-week follow-up visit. These 40 items are used to monitor frequencies of feelings of anxiety.
8. The Snaith-Hamilton Pleasure Scale (SHAPS) [27] will be completed at day 1 of stimulation, day 5 of stimulation, and the 2-week follow-up visit. This scale is used to assess anhedonia.
9. The Beliefs about treatment questionnaires comprises four questions regarding participants expectations.
10. The Rumination scale assess recurring thought process on a 1-4 Likert Scale.
11. Blinding questionnaires for participant and operator are applied at D5.
12. Adverse Event questionnaires are administered after every stimulation session and ask about somatic symptoms/experiences during the tACS application.

8.2 SAFETY AND OTHER ASSESSMENTS

8.2.1 SUICIDAL IDEATIONS AND SUICIDAL BEHAVIOR

Only subjects with a HDRS-17 suicidality item score of <3 and low suicide risk based on the C-SSRS are enrolled in this study. Furthermore, suicidal thoughts and behaviors will be assessed using a brief daily suicide survey (IRB# 14-0600) consisting of three questions. Participants will be asked if they had any thoughts of hurting themselves in the last 24 hours (suicidal ideation, SI) and whether they have hurt themselves in the past 24 hours (suicidal behavior, SB). They will also be asked to rate the severity of their depression on a scale of 1 to 10. Participants receive a link to answer the daily suicide survey on RedCap. To maximize participant's safety the daily suicide survey is send during the follow-up period as well. Responses will be monitored by study personnel daily and the last survey will be administered at the day of follow-up visit. In addition, the C-SSRS [13] will be administered by trained research personnel at screening, D1, D5 and the follow-up session to thoroughly assess suicide risk.

If a participant report experiencing either SI or SB on either tool, research personnel will collect more information from the participant to deliver to either [name] or [name]. Clinical personnel will decide if an acute assessment is required. Acute assessment may include facilitating contact of the subject with their psychiatrist or primary care physician to establish a plan for safety, continued care, and follow-up. If the participant does not have an established provider, [name] or [name] will assist in establishing a care plan. If at any point during the assessment, the participant is deemed an imminent risk of harm to self or others, study personnel will enlist the aid of campus security to ensure that the participant is safely escorted to the Emergency Department for further care. [name] and/or Dr.

[name] will decide if participation should be stopped after the acute assessment. If the participant is hospitalized, their participation will end.

8.2.2 DEVELOPMENT OF MANIA

The Young Mania Rating Scale (YMRS) [28] was designed to assess the severity of manic symptoms at enrolment, with the ability to track changes over the duration of participation. When undergoing treatment for depression, a possible side effect (as inferred from clinical trials with antidepressant medications) is to alter levels of serotonin, potentially associated with mania [29], [30]. Although we do not expect such an event to occur since we are not using a medication that targets serotonin levels, we will be conducting this assessment at Day 1, Day 5 and during the 2-week follow-up as a precautionary measure. If a participant develops any sign of mania (YMRS > 12), [name] will conduct an acute assessment to determine if they are experiencing mania. If this occurs during the week of stimulation, participation in the study will be stopped and their primary mental health care provider or family physician will be contacted. In the case that they do not see anyone for their depression, [name] will assist in creating a medical care plan

8.2.3 ADVERSE EVENT ASSESSMENT

A structured interview probing for the experience of adverse events will be completed after each day of stimulation and at the follow up visit. [name] or [name] will use the completed interview to assess the severity of the adverse event and its relationship to the study intervention as well determine if participation should be terminated.

8.2.4 STIMULATION RELATED SIDE EFFECT ASSESSMENT

A stimulation questionnaire will be administered at the end of each stimulation session. This tool will be used as a safety measure and to collect data on the participant's experience. A similar questionnaire was used in a previous study (IRB# 13-2995) to determine ability to successfully blind the participants using sham transcranial current stimulation.

8.3 ADVERSE EVENTS AND SERIOUS ADVERSE EVENTS

8.3.1 DEFINITION OF ADVERSE EVENTS (AE)

Adverse event means any untoward medical occurrence associated with the use of an intervention in humans, whether considered intervention-related (21 CFR 312.32 (a)).

8.3.2 DEFINITION OF SERIOUS ADVERSE EVENTS (SAE)

An adverse event (AE) or suspected adverse reaction is considered "serious" if, in the view of the investigator, it results in any of the following outcomes: death, a life-threatening adverse event, inpatient hospitalization or prolongation of existing hospitalization, a persistent or significant incapacity or substantial disruption of the ability to conduct normal life functions, or a congenital anomaly/birth defect. Important medical events that may not result in death, be life-threatening, or require hospitalization may

be considered serious when, based upon appropriate medical judgment, they may jeopardize the subject and may require medical or surgical intervention to prevent one of the outcomes listed in this definition. Examples of such medical events include allergic bronchospasm requiring intensive treatment in an emergency room or at home, blood dyscrasias or convulsions that do not result in inpatient hospitalization, or the development of drug dependency or drug abuse.

8.3.3 CLASSIFICATION OF AN ADVERSE EVENT

8.3.3.1 SEVERITY OF EVENT

All adverse events (AEs) will be assessed by the principal investigator and/or co-investigator(s) using the following guidelines:

- **Mild** – Events require minimal or no treatment and do not interfere with the participant's daily activities.
- **Moderate** – Events result in a low level of inconvenience or concern with the therapeutic measures. Moderate events may cause some interference with functioning.
- **Severe** – Events interrupt a participant's usual daily activity and may require systemic drug therapy or other treatment. Severe events are usually potentially life-threatening or incapacitating. Of note, the term "severe" does not necessarily equate to "serious".

8.3.3.2 RELATIONSHIP TO STUDY INTERVENTION

All adverse events (AEs) must have their relationship to study intervention assessed by the principal investigator and co-investigator(s) who examines and evaluates the participant based on temporal relationship and their clinical judgment. The degree of certainty about causality will be graded using the categories below. In a clinical trial, the study product must always be suspect.

- **Definitely Related** – There is clear evidence to suggest a causal relationship, and other possible contributing factors can be ruled out. The clinical event, including an abnormal laboratory test result, occurs in a plausible time relationship to study intervention administration and cannot be explained by concurrent disease or other drugs or chemicals. The response to withdrawal of the study intervention (dechallenge) should be clinically plausible. The event must be pharmacologically or phenomenologically definitive, with use of a satisfactory rechallenge procedure if necessary.
- **Probably Related** – There is evidence to suggest a causal relationship, and the influence of other factors is unlikely. The clinical event, including an abnormal laboratory test result, occurs within a reasonable time after administration of the study intervention, is unlikely to be attributed to concurrent disease or other drugs or chemicals, and follows a clinically reasonable response on withdrawal (dechallenge). Rechallenge information is not required to fulfill this definition.
- **Potentially Related** – There is some evidence to suggest a causal relationship (e.g., the event occurred within a reasonable time after administration of the trial medication). However, other factors may have contributed to the event (e.g., the participant's clinical condition, other concomitant events). Although an AE may rate only as "possibly related" soon after discovery, it can be flagged as requiring more information and later be upgraded to "probably related" or "definitely related", as appropriate.

- **Unlikely to be related** – A clinical event, including an abnormal laboratory test result, whose temporal relationship to study intervention administration makes a causal relationship improbable (e.g., the event did not occur within a reasonable time after administration of the study intervention) and in which other drugs or chemicals or underlying disease provides plausible explanations (e.g., the participant's clinical condition, other concomitant treatments).
- **Not Related** – The AE is completely independent of study intervention administration, and/or evidence exists that the event is definitely related to another etiology. There must be an alternative, definitive etiology documented by the clinician.

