8.3.3.3 EXPECTEDNESS

The principal investigator ([name]), with input from the co-investigator ([name]) when necessary, will determine whether an adverse event (AE) is expected or unexpected in this population. The co-investigator ([name]) is an expert in non-invasive brain stimulation and will provide his expert opinion regarding this as well. An AE will be considered unexpected if the nature, severity, or frequency of the event is not consistent with the risk information previously described for the study intervention.

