8.3.4 TIME PERIOD AND FREQUENCY FOR EVENT ASSESSMENT AND FOLLOW-UP

The occurrence of an adverse event (AE) or serious adverse event (SAE) may come to the attention of study personnel during study visits, or the study subject may report AE or SAEs outside of a scheduled study visit. All AEs including local and systemic reactions not meeting the criteria for SAEs will be captured on the appropriate case report form (CRF). Information to be collected includes event description, time of onset, clinician's assessment of severity, relationship to study product (assessed only by those with the training and authority to make a diagnosis), and time of resolution/stabilization of the event. All AEs occurring while on study must be documented appropriately regardless of relationship. All AEs will be followed to adequate resolution. Any medical condition that is present at the time that the subject is screened will be considered as baseline and not reported as an AE. However, if the study subject's condition deteriorates at any time during the study, it will be recorded as an AE. Changes in the severity of an AE will be documented to allow an assessment of the duration of the event at each level of severity to be performed. AEs characterized as intermittent require documentation of onset and duration of each episode.

Research personnel will record all reportable events with start dates occurring any time after informed consent is obtained until 7 (for non-serious AEs) or 30 days (for SAEs) after the last day of study participation. At each study visit, research personnel will inquire about the occurrence of AE/SAEs since the last visit. Events will be followed for outcome information until resolution or stabilization. All AEs including local and systemic reactions not meeting the criteria for SAEs will be captured on the appropriate case report form (CRF). Information to be collected includes event description, time of onset, clinician's assessment of severity, relationship to study product (assessed only by those with the training and authority to make a diagnosis), and time of resolution/stabilization of the event. All AEs occurring while on study must be documented appropriately regardless of relationship. All AEs will be followed to adequate resolution.

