9.4.4 SAFETY ANALYSES

As discussed in **Section 8.2, Safety and Other Assessments** safety will be assessed with the three questions from the daily suicide questionnaire, the C-SSRS, an adverse effects questionnaire, and the Young Mania Rating Scale (YMRS).

The suicide questionnaire is used as a screening to assess increase in suicidal ideation (SI) or suicidal behavior (SB) daily. The C-SSRS will be used to assess suicide risk more thoroughly. If a participant's responses on either tool indicate SI or SB, the subject will be contacted, and an acute assessment will be completed if deemed necessary by [name] or [name] (as described above). Any verified increases in suicidal ideation will be described in counts/percentages and compared between groups using chi-square tests.

The stimulation questionnaire will be administered following every stimulation session, for a total of 5 administrations per participant. This questionnaire solicits ratings of 14 possible adverse effects associated with electrical stimulation, on a scale of 1 (absent) to 4 (severe). Paired t-tests with random effect "subject" will be calculated per adverse effect to determine if there are any differences in adverse effect severity between groups (sham/placebo, 10 Hz tACS). Severity per adverse effect will be described with mean and standard deviation.

The Young Mania Rating Scale (YMRS) will be used to assess any development of mania over the course of treatment. A YMRS score of greater than 12 indicates the possible development of a manic episode. Any subject who scores greater than 12 on the YMRS will be assessed by [name] or [name]. Any verified manic episode will be described in counts/percentages and compared between groups using a chi-square test.

The Adverse Events Structured Interview will be administered by research personnel following every stimulation session and at the follow up visit, for a total of 6 time points per participant. This interview solicits open-ended descriptions of 11 possible adverse effects a participant may experience in any clinical trial as well as one question of 'any other experiences'. Responses will be reviewed by the clinician and rated as described in **Section 8.3**. Paired t-tests will be calculated per adverse effect to determine if there are any differences in adverse effect severity between groups (sham/placebo, 10 Hz tACS). Severity per adverse effect will be described with mean and standard deviation.3.

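### Section 9.4.4 never analyses adverse events by seriousness, relatedness or expectedness, and it names no safety set, so recorded AEs and SAEs can miss the safety comparison

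*Combined protocol and SAP*

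**What the plan says.** The protocol asks for a full adverse event record. Section 8.3.3.1 grades severity as mild, moderate or severe, and warns that severe is not the same as serious. Section 8.3.3.2 requires causality on five levels: "All adverse events (AEs) must have their relationship to study intervention assessed by the principal investigator and co-investigator(s". Under 8.3.3.3 the principal investigator "will determine whether an adverse event (AE) is expected or unexpected in this population". Section 8.3.4 says "All AEs including local and systemic reactions not meeting the criteria for SAEs will be captured on the appropriate case report form (CRF". It foresees that "the study subject may report AE or SAEs outside of a scheduled study visit", and it runs collection from consent "until 7 (for non-serious AEs) or 30 days (for SAEs) after the last day of study participation".

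Section 9.4.4 opens by saying that "safety will be assessed with the three questions from the daily suicide questionnaire, the C-SSRS, an adverse effects questionnaire" and the YMRS; the AE Structured Interview is added at the end. It plans four arm comparisons:

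- verified increases in suicidal ideation, as counts with chi-square tests;
- severity of each of 14 stimulation-questionnaire items;
- verified manic episodes, as counts with a chi-square test;
- severity of each adverse effect from the interview, which has 11 named effects plus one open item and is given at six time points. A clinician rates the responses under Section 8.3, and then "Paired t-tests will be calculated per adverse effect to determine if there are any differences in adverse effect severity between groups".

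Section 9.3 defines one analysis set, participants who received all five sessions. Section 7.1 lists an adverse event among the reasons to stop stimulation. Section 7.2 replaces participants who received only part of the intervention and then left the study. Section 9.4.4 names no population of its own.

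**The concern.** The protocol has clinicians decide, for every event, whether it was serious, expected and caused by the stimulation. The analysis section uses none of those judgements. A reader of the results would expect to learn how many participants in each arm had any AE, a related AE or an SAE, and the plan produces none of these numbers.

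The trial could therefore report no difference in mean severity between arms while its most serious events, and those attributed to stimulation, appear only in case report forms and IRB correspondence. The completer set could add to this, because the participants most likely to be missing from it include those whose stimulation was stopped for an adverse event.

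**Working it through.** **1. What is recorded against what is analysed**

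| Item | Recorded under | Arm comparison in 9.4.4 |
|---|---|---|
| Severity | 8.3.3.1, 8.3.4 | Yes, mean severity of interview items; the stimulation questionnaire has its own 1 to 4 scale |
| Relatedness | 8.3.3.2, 8.3.4 | None |
| Expectedness | 8.3.3.3 | None |
| Seriousness | 8.3.2, 8.3.5 | None |
| Suicidal ideation, mania | 8.2.1, 8.2.2 | Yes, counts of verified cases |
| Events reported outside the interview | 8.3.4 | None, unless verified suicidal ideation or mania |
| AEs that led to stopping | 7.1 | None |

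No other section plans a by-arm count or listing of AEs or SAEs.

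**2. The time window**

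The last interview is at the follow-up visit, Day 22 in the Schedule of Activities (plus or minus 3 days). If that visit is the last day of participation (my assumption), collection runs to Day 22 + 7 = 29 for non-serious AEs and Day 22 + 30 = 52 for SAEs. The SAE window thus extends 30 days past the last interview, against 21 days from Day 1 to Day 22.

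**3. Can mean severity stand in for a count?**

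Take 10 per arm (9.2). Let one participant in one arm score d above the floor on an item, and let everyone else in both arms score the floor.

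- Difference in means: d/10.
- Sum of squares in the affected arm: d² × (1 − 1/10) = 0.9d²; in the other arm, 0.
- Pooled variance: 0.9d²/18 = 0.05d².
- Standard error: √(0.05d² × 2/10) = 0.1d.
- t = (d/10)/(0.1d) = 1 on 18 degrees of freedom, two-sided p = 0.33.

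The size d cancels, so a mild and a severe event give the same result. The plan calls these paired tests although the arms are independent. With ten arbitrary pairs the differences are one d and nine zeros: mean d/10, standard error 0.1d, again t = 1 (9 degrees of freedom, p = 0.34). A single serious event that does reach the interview is not visible in the test, and the severity score would not identify it as serious.

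**4. Would counts be testable?**

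Barely. Fisher's exact test at 10 v 10 gives p = 0.087 for 4 v 0 and first falls below 0.05 at 5 v 0 (p = 0.033). The chance of at least one event in an arm of 10 is 1 − (1 − p)^10:

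| Assumed true rate | Chance of at least one event in 10 |
|---|---|
| 1% | 9.6% |
| 5% | 40.1% |
| 10% | 65.1% |
| 20% | 89.3% |

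The documents give no SAE rate, so these rates are assumptions. An exact two-sided 95% interval for no events in 10 has an upper limit of 1 − 0.025^(1/10) = 30.8%. The missing analysis is therefore a descriptive table with intervals and a listing, not another test.

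**5. The analysis set**

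Section 9.3 carries completers forward into all analyses, says that those who do not complete are replaced, and expects 20 analysable participants. Section 7.1 allows an AE to end stimulation. Reading these together, and with no separate set named in 9.4.4, a participant stopped for an AE can be absent from the safety comparison.

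**The case against.** The strongest reply is that the plan is not silent on adverse events, and much of that reply stands. A reader might infer that related AEs and SAEs never enter any arm comparison. The documents do not support this. Events elicited at the interview, related ones included, enter through their severity. The open item takes the interview beyond its 11 named effects, and under 8.3.4 staff ask at every visit about events since the last one. Verified suicidal ideation and mania are counted by arm, and such an event could also be an SAE. What does stand is that none of these events is analysed as related, serious or unexpected.

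Three other stronger readings should also be set aside.

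- Section 8.2.1 says "If the participant is hospitalized, their participation will end", which might suggest that anyone hospitalised after Day 5 loses the follow-up interview. The sentence closes the suicidality pathway, and no section extends it to other hospitalisations. The point does not need it.
- It might be inferred that an omitted SAE would appear as 0/10. It would not: 9.4.4 has no SAE row, so the plan would show nothing.
- The increased suicidal thoughts in four sham participants of the earlier trial (2.3.1) might seem to show what would be missed. Section 9.4.4 already compares that category, and 2.3.1 does not call those events serious.

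It is also fair to say that the record has other uses: IRB reporting (8.3.5), the response to unanticipated problems (8.4.2), study suspension (10.1.2) and safety review by the principal investigator (10.1.6). These protect participants during the trial, but none of them reports safety by arm.

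Finally, 7.1 keeps participants who stop stimulation in the study procedures and invites them to follow-up, so their data may exist. That makes a wider safety set feasible, but it does not put them in the set that 9.3 defines.

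**Conclusion.** The point holds in this form: seriousness, relatedness and expectedness are recorded for AEs but have no planned analysis; CRF events outside the interview or after follow-up have no planned comparison unless they are verified suicidal ideation or mania; and participants stopped for an AE can drop out because the only defined set is five-session completers.

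This is more than missing detail, because the one comparison that does cover general AEs gives t = 1 and p = 0.33 for a lone raised score of any size. That figure assumes 10 per arm, everyone else at the floor, and a two-sided test (the plan does not state sidedness). The loss of stopped participants rests on reading 9.3 as governing the safety analyses, since 9.4.4 names no other set. How many events would be missed cannot be estimated from the documents. The plan should be changed, but the EEG analyses are not affected.

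**What to change.** In 9.4.4, define a safety set of all randomised participants who received any stimulation, active or sham, including those later replaced. Denominators may then exceed 10 per arm.

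Add one descriptive by-arm table built from the 8.3.4 case report forms over the full collection window, including the 7 and 30 days after participation. Count participants with at least one:

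- AE of any kind;
- related AE (graded definitely, probably or potentially related);
- unexpected AE;
- severe AE;
- SAE;
- AE leading to stopping stimulation.

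Give an exact 95% interval for each proportion, with no test required. List every SAE by arm with its relatedness grade. Mark events that began before the first session, since collection starts at consent. Keep the questionnaire and interview severity scores as supporting detail.

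The cost is plan wording, one table and one listing from data already collected. No new data, visits or participants are needed.
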